Scalar Closed-Loop STN / GPi DBS Based on Evoked and Spontaneous Potentials (Intraoperative Studies)

NCT03270657

Document Date: March 8, 2019

Purpose of the Study

The purpose of this study is to measure neural activity during deep brain stimulation (DBS). There are two types of neural activity that we will record from DBS electrodes during this study: DBS local evoked potentials (DLEPs) and spontaneous, local field potentials (LFPs). We will measure the effects of varying stimulation parameters on both the neural activity and changes in motor symptoms -- bradykinesia and tremor -- in subjects with Parkinson's disease (PD). Correlating neural activity characteristics with changes in symptoms will improve our understanding of the mechanisms of action of DBS. This intraoperative study will specifically compare our ability to record neural activity using circuitry developed at Duke for this purpose [Kent et al, 2015] to a new, implanted pulse generator (IPG; RC+S) developed by Medtronic. These intraoperative studies will specifically test a preliminary version of the RC+S (that is not designed for implantation), and will lead to a clinical trial assessing the efficacy of the implantable RC+S IPG in PD patients once this device is available and approved for this trial.

Background and Significance

Deep brain stimulation (DBS) is a surgical intervention that is effective in treating movement disorders, particularly Parkinson's disease (PD). A battery-powered IPG, placed in the patient's chest, delivers electrical stimulation to a connected brain electrode typically implanted in the subthalamic nucleus (STN) or globus pallidus internus (GPi). Despite the clinical effectiveness of DBS, the underlying physiological mechanisms of action remain unclear and there is no capability for device self-adjustment or responsiveness to patient symptoms, limiting the full optimization of this treatment.

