Stimulation parameters (amplitude, frequency, and pulse width) are programmed after surgery and at follow-up intervals, and the efficacy of DBS depends on finding parameters that reduce symptoms without causing side effects. However, there are over 42,000 available combinations of amplitude, frequency, and pulse width in the IPG, and few data describing the relationships between stimulation parameters and clinical outcomes. As a result, the selection of stimulation parameters is an ad hoc process, with associated difficulties of time, expense, and patient discomfort. Further, the patient is often deprived of the optimal benefits of stimulation until this time consuming process leads to efficacy.

Application of each DBS pulse results in activation of a population of neurons around the electrode. This evoked neuronal activity creates a signal -- the DBS local evoked field potential (DLEP) -- that can be recorded with two of the four contacts on either the clinical DBS electrode or a second electrode. Thus, this intraoperative recording approach does not require implantation of any electrical hardware. The magnitude and character of the DLEP response will reveal the type and spatial extent of neuronal element activation during stimulation, including between brain regions, such as between subthalamic nucleus (STN) and globus pallidus externa (GPe). Our previous work exploring the mechanisms of action of DBS revealed a very strong correlation between the number and type of activated neurons and clinical efficacy during variation in stimulation intensity [Kuncel et al, 2007; Kent et al, 2015]. Therefore, we expect a strong correlation between the recorded DLEP and the changes in symptoms during DBS. Spontaneous, local field potentials (LFPs) are also recorded using the same methods described above. LFPs are signals measured with electrode contacts that are continuously generated by ongoing neural activity, whereas DLEPs are short-duration signals evoked immediately following stimulation pulses. Together, DLEPs and LFPs are a potential biomarker for disease state and severity in PD, which we will

test initially intraoperatively and long-term using the RC+S IPG for scalar closed-loop control of the DBS parameters.

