We will measure tremor and/or bradykinesia in persons with PD during DBS. Subjects will be familiarized with and able to practice the evaluation tasks before preparation for surgery. Further, they will be asked to discontinue use of dopaminergic and/or anti-tremor medications overnight prior to the study (as is the clinical routine for this procedure), to reduce variability of motor symptoms due to the time course of medications. We will conduct evaluations using unilateral stimulation, with the limb contralateral to the side of stimulation used for measurement of motor symptoms. Subjects may also be asked to rate any side effects that they experience on a 0 - 10 scale.

Contacts on the subject's DBS electrode will be used for stimulation and recording, with a second electrode in either STN or GPi/GPe used for recording. The four DBS contacts are designated as 0-1-2-3 in the ventral-dorsal direction. For monopolar stimulation, a single contact will be used for cathodic stimulation (1- or 2-) and a conductive pad will be placed on the subject's skin, outside of the sterile field, to serve as the return electrode. The recording contacts will be two other contacts on the DBS lead. For bipolar stimulation, DBS pulses will be applied between two electrode contacts, and the recording contacts will be the two remaining free contacts. The stimulus waveform will be a charge-balanced biphasic pulse, with charge restricted to values below the limit set by the manufacturer, 30 $\mu\text{C}/\text{cm}^2$. Another conductive pad will be placed on the subject to serve as the recording reference. The

DBS lead cannula or a surgical retractor normally placed at the cranial incision site may also be used as the recording reference or return electrode.

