In subjects with tremor-dominant PD, we will record both the tremor and DLEP and/or LFP responses from the DBS electrode(s). Several trials will be conducted with different stimulation amplitudes, frequencies (≤ 185 Hz), temporal patterns, and contact configurations. The stimulation amplitude will be less than that identified to be uncomfortable to the subject or that generates side effects, as determined by a neurologist and/or neurosurgeon during the initial testing phase following implantation. The different stimulation parameters will be delivered in randomized order, and the subject will be blinded to the parameters. Measurements will be made during 2-minute trials, in which stimulation will be off for the first minute of the trial, and on for the remaining minute. At 30 s into both the off (baseline) and on phases of the trial, tremor will be measured for 20 s. The neural activity will also be measured from the electrode during both the off and on phases. The total amount of time necessary for data collection will be about 45 minutes.

Tremor will be measured using an accelerometer taped to the back of the subject's hand, and with the wrist extended such that the hand is parallel to the forearm. The elbow may either be supported or unsupported, depending on which induces greater tremor (determined prior to any trials in each subject). Tremor as measured by an accelerometer correlates well with clinical tremor rating scales [Elble et al, 2006].

In subjects with Parkinson's disease who do not have dominant tremor symptoms, we will record both bradykinesia testing responses and DLEP and/or LFP potentials. Several trials will be conducted with different stimulation amplitudes, mean frequencies (≤ 185 Hz), temporal patterns, and contact configurations. The maximum amplitude delivered will be determined as described as above. The different stimulation parameters will be delivered in randomized order, and the subject will be blinded to the parameters. Measurements will be made in 10-minute trials, in which stimulation will be off for the first five minutes of the trial, and on for the remaining five minutes. At approximately 90, 210 and 250 s into both the off (baseline) and on phases of the trial, bradykinesia will be measured for 20 s. The neural activity will also be measured from the electrode during both the off and on phases of the trial. The total amount of time necessary for data collection will be about 45 minutes.

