The data set will consist of recordings of neural and/or LFP recordings, and either mouse click timing data for measurement of bradykinesia in Parkinson's disease subjects or tremor accelerometry data for patients with Parkinson's disease. The DLEP recordings will be serially averaged with stimulus-triggering to remove random noise while preserving the evoked response. The signal-to-noise ratios of DLEP recordings will be compared across data sets to determine which combination of stimulation and recording sites maximize recording quality. We will quantify performance on the mouse click timing task by the delay between key presses and the time each key is held. Tremor will be quantified by calculating the total power within a window of the power spectrum of the time series of the tremor. We will perform ANOVA and post-hoc statistical analysis, in which the amplitude, frequency, and contact configuration used for stimulation will be the independent variables, and with dependent variables describing bradykinesia, tremor, and DLEP characteristics. We will also calculate correlation coefficients between tremor or bradykinesia and DLEP characteristics. Data and statistical analyses will be conducted by the study team, including the study statistician, [name] (Associate Professor of Biostatistics and Bioinformatics).

Additionally, clinical study staff may use pre- and post-operative brain imaging to determine the location of implanted DBS electrode contacts. The only data generated from this analysis will be a determination of the location of the contacts used to record neural activity (DLEPs and/or LFPs) relative to the brain region targeted for stimulation. Other study staff will analyze DLEP and/or LFP recordings obtained during surgery to generate a prediction of recording contact location prior to imaging analysis for each subject, and clinical study staff will be blinded to these predictions during imaging analysis.

Subjects will be included in data analysis if DBS is clinically effective at reducing motor symptoms for particular stimulation parameters, and DLEP and/or LFP data are observed during at least one trial.

[name] and [name] [name] conduct a total of 4-6 new DBS implants for PD per month. We have recruited approximately 1 subject per month at Duke over the past 18 months to participate in other intraoperative studies. Thus, we expect to recruit a maximum of 32 subjects during the course of this study at Duke University.

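### Each trial records an OFF (baseline) symptom reading, but the ANOVA and the DLEP-symptom correlations give it no stated role; it should enter as a covariate in a model that includes subject.

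*Combined protocol and SAP*

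**What the plan says.** The purpose, in Purpose of the Study, is to measure "the effects of varying stimulation parameters on both the neural activity and changes in motor symptoms -- bradykinesia and tremor". Background and Significance gives the hypothesis: "we expect a strong correlation between the recorded DLEP and the changes in symptoms during DBS". Both are about change.

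Study Design and Procedures builds a baseline into each trial. A tremor trial is one minute off then one minute on: "At 30 s into both the off (baseline) and on phases of the trial, tremor will be measured for 20 s". A bradykinesia trial is five minutes off then five minutes on, with readings at about 90, 210 and 250 s in "both the off (baseline) and on phases of the trial, bradykinesia will be measured for 20 s". The order of settings is randomized and the session lasts about 45 minutes.

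Data Analysis and Statistical Considerations is the only analysis text. In its ANOVA, "the amplitude, frequency, and contact configuration used for stimulation will be the independent variables, and with dependent variables describing bradykinesia, tremor, and DLEP characteristics". It adds: "We will also calculate correlation coefficients between tremor or bradykinesia and DLEP characteristics". Tremor is spectral power in a window; bradykinesia is key-press delay and hold time. No phase is named for either outcome, no OFF term or change score is defined, and no subject term is listed. The one rule that implies a comparison with no stimulation selects subjects and does not define an outcome: "Subjects will be included in data analysis if DBS is clinically effective at reducing motor symptoms for particular stimulation parameters".

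**The concern.** The aim is change, a baseline is collected to measure it, and the analysis text does not connect the two. ON alone, raw change, percent change and ON adjusted for OFF all fit the section as written. They can give different precision and different correlations, and the choice could be made after the data are seen.

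About half of each session is spent on OFF phases. With at most four full bradykinesia trials per subject, precision is scarce. If OFF and ON readings in the same trial share variation within a subject, the OFF reading can remove that part from the comparison of settings. The protocol already treats one source of symptom variability as a nuisance: medication is withheld overnight "to reduce variability of motor symptoms due to the time course of medications". That does not show how much shared variation remains from trial to trial.

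The symptom ANOVA and the DLEP-symptom correlations are affected. The comparison of the two recording systems and the signal-to-noise analysis are not.

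**Working it through.** **The plan's own figures.** There is no power calculation, SD or OFF-ON correlation to reproduce. The protocol's timings give floor(45/2) = 22 tremor trials with 22 × 1 = 22 min OFF, or floor(45/10) = 4 bradykinesia trials with 4 × 5 = 20 min OFF. Maximum enrolment is 32.

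**Assumed inputs.** r is the within-subject OFF-ON correlation at a given setting: 0, 0.3, 0.5, 0.7. K is the within-subject ON SD divided by the OFF SD. Subjects n = 8, 16, 32. Settings m = 2 or 4 with T = 4 trials, and 2 or 11 with T = 22.

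**1. OFF as covariate, against ON-only, both with a subject term and one OFF slope for all settings.** SE ratio = √[(1−r²)(v−1)/(v−2)], with v = nT − n − (m−1).

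Example: n = 8, T = 4, m = 4 gives v = 32 − 8 − 3 = 21. At r = 0 the ratio is √(20/19) = 1.026; at r = 0.7 it is √(0.51 × 20/19) = 0.733.

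| r | SE ratio, range over n, T, m | Equivalent extra trials, 1/(1−r²) − 1 |
|---|---|---|
| 0 | 1.001-1.026 | 0% |
| 0.3 | 0.955-0.979 | 10% |
| 0.5 | 0.867-0.889 | 33% |
| 0.7 | 0.715-0.733 | 96% |

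**2. Raw change score, against ON-only, with a subject term.** SE ratio = √(1 + 1/K² − 2r/K), which exceeds 1 when r < 1/(2K).

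| K | r = 0 | 0.3 | 0.5 | 0.7 | Worse than ON-only when |
|---|---|---|---|---|---|
| 1 | 1.41 | 1.18 | 1.00 | 0.77 | r < 0.5 |
| 0.75 | 1.67 | 1.41 | 1.20 | 0.95 | r < 0.67 |
| 0.5 | 2.24 | 1.95 | 1.73 | 1.48 | always |

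**3. The section read literally, without a subject term.** Take K = 1 and let b be the between-subject SD divided by the within-subject SD, with the subject level shared by both phases. Residual-SD ratios against ON-only are √[2(1−r)/(1+b²)] for change and √(1−R²) for the covariate, where R = (b²+r)/(b²+1).

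| b (assumed) | Form | r = 0 | 0.3 | 0.5 | 0.7 |
|---|---|---|---|---|---|
| 1 | change | 1.00 | 0.84 | 0.71 | 0.55 |
| 1 | covariate | 0.87 | 0.76 | 0.66 | 0.53 |
| 2 | change | 0.63 | 0.53 | 0.45 | 0.35 |
| 2 | covariate | 0.60 | 0.51 | 0.44 | 0.34 |

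Here change is no worse than ON-only whenever b² + 2r ≥ 1. The covariate is still slightly better.

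**4. Scale for tremor.** Step 1 needs a common OFF slope. If settings suppress tremor power proportionally, the slope on raw power differs by setting. Simulations with lognormal power, gains from 1 down to 0.1, 16 subjects and a subject term (all assumed), at log-scale r of 0.5 and 0.7, gave covariate SE ratios of about 0.83-0.99 on raw power and 0.70-0.89 on log power.

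**5. Correlations, illustration only.** Assume a within-subject DLEP-ON correlation of 0.50, r = 0.7 and DLEP unrelated to OFF. With k = 0.25/0.75 = 1/3:
- Adjusted: √[k/(k + 1 − 0.49)] = 0.63.
- Raw change: √[k/(k + 0.6)] = 0.60 at K = 1, and √[k/(k + 2.2)] = 0.36 at K = 0.5.
- If DLEP and OFF correlate at q = ±0.2, the adjusted value is (0.5 − qR′)/√[(1−q²)(1−R′²)] with R′ = 0.7√0.75 = 0.606. That gives 0.49 at +0.2 and 0.80 at −0.2.

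**6. Carry-over into OFF.** If a fraction f of the preceding trial's effect persists, a contrast between settings in random order is exaggerated by f × slope/T. The slope is rK for the covariate and 1 for raw change. With f = 0.5 (assumed), r = 0.3 to 0.7 and K = 0.5 to 1:
- T = 4: 0.5 × 0.15/4 = 1.9% to 0.5 × 0.7/4 = 8.75%; raw change 0.5/4 = 12.5%.
- T = 22: 0.3% to 1.6%; raw change 2.3%.

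**The case against.** The strongest reply is that the protocol labels the OFF phase as baseline and states its aim as changes, so a comparison with OFF is plainly meant and one line defining the response would do. Much of this stands. A reader might infer that the investigators decided to ignore the baseline; the documents do not support that. But intent does not fix the form, and the forms differ in precision.

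A second reply is that the warning against raw change rests on a subject term the analysis section never states. This also stands. A reader might infer from step 2 that a change score would be worse than ignoring OFF under the plan as written. Step 3 shows that this does not generally follow when subject is left out. The subject term therefore has to be part of the fix, not assumed silently.

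Third, the gain is not established: r is unknown, the benefit at r = 0.3 is only 2% to 4.5% in SE, and the adjusted correlation can fall just below the unadjusted one (0.49 against 0.50). That is correct, and the sizes are conditional for that reason. The point about tremor scale also stands, so log power belongs in the fix.

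Fourth, carry-over. Twenty-two trials in 45 minutes leaves no gap, so tremor OFF would be read 30 s after stimulation stops. The assurance in Risk / Benefit Analysis that symptoms return to earlier levels covers worsened symptoms, not persisting benefit. This remains an open limitation. It affects raw change more than the covariate when the slope is below 1.

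**Conclusion.** The point holds as a gap in the stated analysis: a baseline is collected in every trial and given no stated role in the ANOVA or the correlations.

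A reader might also infer that the setting comparisons are biased. They are not on this account, because settings are delivered in randomized order. What is lost is precision, together with a fixed definition of the response.

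The size depends on r, which the documents do not give. Against ON-only with a subject term and a common OFF slope, the gain runs from nothing at r = 0 to a standard error about 27% to 28% smaller at r = 0.7. It can be much less on raw tremor power. The change is worth making because it costs almost nothing. Confidence is medium, since the gap is clear and the benefit is not known.

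**What to change.** In Data Analysis and Statistical Considerations, state:

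> Each trial's symptom response (the ON value, or the change from OFF to ON) will be analysed with the same trial's OFF value as a covariate, in a model that includes subject. Tremor power will be log-transformed in both phases. For bradykinesia the OFF value will be the mean of the OFF-phase readings. DLEP-symptom correlations will use the same adjusted response, as partial correlations given subject and OFF value.

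Change from OFF can remain the reported effect. With OFF in the model, using ON or change as the response shifts only the OFF coefficient, by one; setting effects and partial correlations are identical. For tremor, change is then on the log scale.

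The cost is wording and about one degree of freedom per outcome, with no new data. If r = 0, the SE loss is 0.5% to 2.6% with 4 trials and 0.1% to 0.3% with 22 (32 down to 8 subjects). The section should also acknowledge that persisting benefit from the preceding trial could enter the OFF value.

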The shape and magnitude of DLEPs and LFP activity may also be sensitive to DBS electrode location, and this dependence suggests that they may assist with targeting brain structures during DBS implant surgery as well as post-operative selection of stimulation contacts and dynamic adjustment of stimulation parameters [Kent et al., 2015; Chen et al., 2006]. We therefore expect that DLEP and/or LFP characteristics will vary with the placement of DBS electrode relative to the brain regions targeted for stimulation.

Study Design and Procedures

We will measure DBS local evoked potentials (DLEPs) and/or local field potentials (LFPs) together with motor symptoms (tremor and/or bradykinesia) in response to deep brain stimulation (DBS). The study will be conducted in the operating room at Duke University Medical Center. Additional operating room costs will be covered by institutional resources at Duke. The study will be performed on subjects who are undergoing implantation of the DBS system during an awake, stereotactic procedure for PD.

The subject group will only include patients undergoing a DBS implant procedure for PD. The surgical procedure will proceed as needed for treatment of Parkinson's disease (PD), including implantation of the DBS electrode (one into STN or dual electrodes into STN and GPi/GPe) into the targeted regions of the brain. For this research, subjects will receive temporary (~45 min) percutaneous extensions to the DBS electrode(s) and DBS lead cannula after implantation. These temporary extensions will connect to both our Duke stimulation and recording system or the Medtronic RC+S test recording system, alternating as needed, to allow recording and direct comparison of neural DLEP responses and/or LFPs using the two different stimulation/recording systems. Details of the stimulation and recording system are provided in the Study Interventions section. After the study is completed, the second DBS electrode (if placed) and the temporary percutaneous extensions will be removed. Then, the ordinary clinical conduct of the procedure will continue for treatment of the patient's movement disorder.

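### The optional contact-location exercise has no reference prediction made without recordings and does not say what predictors may see, so agreement with imaging could partly reflect the surgical plan.

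*Combined protocol and SAP*

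**What the plan says.** The exercise is described in the second paragraph of Data Analysis and Statistical Considerations. Clinical study staff may use pre- and post-operative imaging to locate the recording contacts "relative to the brain region targeted for stimulation". Separately, "Other study staff will analyze DLEP and/or LFP recordings obtained during surgery to generate a prediction of recording contact location", and they do so "prior to imaging analysis for each subject". The imaging side is masked: "clinical study staff will be blinded to these predictions during imaging analysis".

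Three statements in Study Design and Procedures bear on what is known without any recording:
- Contact numbering: "The four DBS contacts are designated as 0-1-2-3 in the ventral-dorsal direction".
- In bipolar stimulation, "the recording contacts will be the two remaining free contacts", so the stimulation setting identifies the recording pair.
- The research does not change where the electrode is placed.

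The motivation is in Background and Significance, which says of the DLEP and LFP signals that "they may assist with targeting brain structures during DBS implant surgery". It also expects signal characteristics to vary with electrode placement.

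The documents do not say whether predictors know the target, the contact numbers or the stimulation configuration. They give no accuracy measure, no chance level and no comparison prediction.

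**The concern.** The two stated safeguards work in one direction. Predicting first keeps the imaging result from the predictors, and masking the imaging readers keeps them from anchoring on the predictions. Neither ensures that a prediction comes from the signal.

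Information about the answer exists before any trace is read. The intended nucleus is known, the contact number gives order along the lead, and the lead was aimed at the region against which location is then judged. A predictor with this information could do better than chance while learning nothing from the recording.

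At stake is the interpretation of a good result. If the exercise is to support the idea that these signals could help with targeting, the recordings must add something to the plan that the surgical team already holds. Agreement with imaging, reported alone, cannot separate a signal that locates the contact from a lead that went where it was aimed.

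**Working it through.** **No figure to reproduce.** The plan gives no accuracy target, reference accuracy, alpha or power for this exercise. The maximum of 32 subjects is supported by recruitment rates, not by a power calculation.

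**The text set side by side.**

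| Possible source of agreement | Stated protection |
|---|---|
| Predictor has seen the imaging result | Yes: prediction comes first, by separate staff |
| Imaging reader has seen the prediction | Yes: reader is masked |
| Predictor knows the surgical target | None stated |
| Predictor knows the contact number or stimulation setting | None stated |
| Benchmark for what the plan alone would achieve | None stated |

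The analysis-set rule may add to the problem. Subjects are analysed only if DBS reduces motor symptoms at some setting, which may favour well-placed leads and so make a plan-only guess more accurate. The documents do not show by how much.

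**Illustration of why the benchmark matters.** Every input except n is an assumption: one right-or-wrong prediction per subject, n = 32 (the maximum in Selection of Subjects), one-sided alpha 0.025, and plan-only accuracy p ranged over 50% to 80%. The formula is the exact binomial tail, P(X ≥ c) = Σ C(32, k) p^k (1 − p)^(32 − k) for k = c to 32. Here c is the smallest count whose tail probability under the chosen benchmark is at most 0.025.

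Probability that a predictor who ignores the recordings passes:

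| Benchmark | c | p = 50% | p = 60% | p = 70% | p = 80% |
|---|---|---|---|---|---|
| 25% (one of four positions) | 14/32 | 0.81 | 0.98 | 0.999 | 1.00 |
| 50% | 23/32 | 0.01 | 0.12 | 0.50 | 0.91 |

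Against its own accuracy as benchmark, the same predictor passes with probability 0.010 (p = 50%, c = 23), 0.025 (60%, c = 25), 0.019 (70%, c = 28) or 0.007 (80%, c = 31). With no plan-only benchmark, the chance of a spurious success ranges from negligible to near certain, depending on two quantities that the plan does not fix. With one, it stays within alpha.

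**What a fair benchmark costs in power.** If true accuracy with recordings is 90%, power against a fixed benchmark of 50%, 60%, 70% or 80% is 0.999, 0.99, 0.79 or 0.16. If the plan alone already performs well, 32 subjects may not settle the question, so an interval is more useful than a pass mark. Imaging analysis is optional, so fewer than 32 may be evaluable. Several contacts in one subject would be correlated, which the illustration ignores.

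**The case against.** The case on the other side is substantial, and several parts of it stand.

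- **Silence is not exposure.** A reader might infer that predictors know the target and contact numbers. The text says only that they are other staff working from recordings. It does not say whether they were in the operating room or what labels their files carry. The supportable statement is that masking is not stated.
- **The size is unknown.** A reader might also infer that a plan-only guess is usually right, and put 70% to 90% on it. That presumes an in-target or out-of-target endpoint, which the plan does not define; location could equally be graded by distance or depth. Aiming a lead at a nucleus does not establish where each of four contacts lies. This stands, and it is why the figures above are only an illustration.
- **The exercise is peripheral.** It is introduced as an addition, its imaging is optional, and targeting appears as background rather than in the stated purpose. This also stands, and it limits the weight of the point.
- **Stripping labels may do harm.** Study Interventions describes differential recordings between two contacts, and the recording pair depends on the stimulation configuration. Removing contact numbers and shuffling channels may discard geometry needed to read the signal. In practical targeting use, target and contact number would be known anyway. Such masking is a debatable trade-off and should not be required.

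None of this supplies the missing comparison. A plan-only reference addresses added value whether or not predictors are masked.

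**Conclusion.** The point holds as a gap in an optional, secondary analysis. The plan protects the imaging reading well. It does not state what predictors know and has no recording-free reference, so agreement with imaging would not by itself show that the signals carry location information. The conclusion rests on three features of the text: location is defined relative to the target, contact number gives ventral-dorsal order, and placement follows clinical targeting.

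The documents do not allow the size to be derived. They support the statement that agreement could partly reflect the surgical plan, not that it will. Nor do they support reading this as a fault in the ANOVA or in the correlations between neural activity and motor symptoms, which do not use the location predictions.

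**What to change.** Add the following to Data Analysis and Statistical Considerations:

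1. For each subject, before imaging analysis, record a reference prediction made from planned target and contact number only, without the recordings.
2. Fix in advance one measure of agreement with imaging, suited to how location will be expressed.
3. Score the reference prediction and the recording-based prediction against imaging with that measure. Report the paired difference with an interval computed at subject level, so that several contacts in one subject are not counted as independent.
4. State what predictors may see: target, contact number, stimulation configuration and surgical plan.

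The cost is one added comparison, with no extra staff, procedure or burden on subjects. The downside is that the apparent value of the recordings may be smaller than raw agreement would suggest, and the interval may be wide at 32 subjects or fewer. This is a cheap improvement. The reference prediction should be recorded at the time, because one constructed after the imaging is known would be less credible.
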